- **Approach bias modification in alcohol dependence: Do clinical effects replicate¹¹?** This study aimed to replicate and extend the previous study. Alcohol-dependent patients (N=509) received inpatient CBT and were randomly assigned to ABR or no training. The group receiving ABR developed alcohol-avoidance behavior and reported significantly lower relapse rates at one-year follow-up (see Figure 3). Change in alcohol-approach bias mediated this effect. These findings indicate that ABR can be employed to enhance CBT by modifying approach bias.
- **Reducing approach bias to achieve smoking cessation: a pilot randomized placebo-controlled trial¹⁴**. This study aimed to provide a preliminary test of the efficacy of a brief cognitive bias modification program for reducing approach bias in adult smokers motivated to quit. Participants were 52 smokers who were randomly assigned to four sessions of ABR (experimental) or CTRL training (control). Participants were asked to make a self-guided quit attempt upon completion of the final training session. Approach bias was assessed at baseline and at the end of each session, and days abstinent was assessed 1-week following the quit attempt. Individuals assigned to the experimental evidenced significantly greater reductions in approach bias relative to those in the control condition ($p<.001$; see Figure 4). Baseline approach bias did not moderate the between-group effect ($p>.41$); however, higher levels of approach bias at baseline were associated with greater approach bias reduction over time ($p<.001$). Consistent with prediction, the reduction in approach bias during the intervention period was significantly related to the number of days abstinent following the quit attempt ($p=.033$; see Figure 5). These findings extend recent work in alcohol use disorders by showing that approach bias reduction, in this case for smoking-related stimuli, may also facilitate smoking cessation.

Figure 3. Effect of ABR on Alcohol Relapse (Replication)

[figure not shown]

Figure 4. Effect of ABR on Approach Bias (Smoking)

[figure not shown]
[figure not shown]

Figure 5. Approach Bias Reduction and Abstinence (Smoking)

C2. Study Overview and Experimental Design

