Per study protocol (i.e., pre-registered hypotheses and analyses as published in [name] et al., 2019), multivariate generalized linear mixed modeling (GLMM) using a binomial distribution and a logistic linking function was employed to analyze change in biochemically-verified PPA and PA over time. We used multivariate GLMM (with PA and PPA as the multiple dependent variables [DVs]) because multivariate mixed models have greater power than univariate mixed models (Hox et al., 2017) and because assessments at each time point are included as long as at least one of the DVs is available at that time point. Hereafter, we use the general term “abstinence” to refer to the multivariate outcome of PPA and PA.

As in previous smoking research (O’Cleirigh et al., 2018; [name] et al., 2021), we used a piecewise growth curve model to model abstinence over the 18-week study period. This model comprised the pre-quit treatment phase (weeks 1–6), a discontinuity (jump) in abstinence during the quit attempt (between weeks 6–7), and the post-quit follow-up phase (weeks 7–18). The GLMM included a diagonal matrix for the covariance of the errors of the repeated measures and associated random effects. Treatment group was included as a moderator of the discontinuity (jump) in abstinence and the slope of change in abstinence during the post-quit follow-up phase. As per our registered analysis plan ([name] et al., 2019), to minimize Type II error and to provide more stable (replicable) and parsimonious models that fit the data, we recomputed the final multivariate GLMM model after removing non-significant interaction terms (sensitivity analyses showed that results did not change if we did not remove these non-significant interactions).

To examine our pre-registered analysis for whether the intervention was effective in changing avoidance tendencies, we used intent-to-treat multilevel modeling (MLM) to analyze the growth curve of avoidance tendency scores over the 7 weeks of ABR. Since the change over time in avoidance tendency scores may not be linear, we examined linear, quadratic, and logarithmic models for the change over time and selected the model that best fit the data (lowest Akaike Information Criterion [AIC] and lowest Bayesian Information Criterion [BIC]) since failing to do so can lead to incorrect results. In exploratory analyses, we examined whether the initial avoidance tendency score moderated the intervention efficacy.

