As per our pre-registered analysis plan ([name] et al., 2019), we examined the equivalence of the treatment groups on demographic and key psychological variables prior to treatment; variables on which the groups differed were included as covariates in the final analyses if they were significantly related to outcome. The only variable that differed between groups was the initial avoidance tendency score ($t(94) = 2.88$, $p = 0.005$), which was added as a covariate in all analyses. A priori power analysis indicated greater than 0.80 power to detect a significant condition effect if the abstinence rate in ST+ABR was 42 % or greater (effect size $\omega = .238$) with a sample size of 100 (see [name] et al., 2019 for more details).

PROTECTION OF HUMAN SUBJECTS

Risks to Subjects

Human Subjects Involvement and Characteristics

We plan to enroll 100 participants total. The participant population will be comprised of both males and females of mixed ethnic and socioeconomic backgrounds. All participants meeting entrance criteria will be offered the opportunity to participate. Participants will not be excluded on the basis of gender or race. Inclusion and exclusion criteria are presented in the Figure 7.

Figure 7. Study Entry Criteria

| Inclusion Criteria | |
|-------------------------------|---|
| 18 to 65 years old | |
| Informed consent | The capability and willingness to give written informed consent, to understand inclusion and exclusion criteria, and to accept the randomized group assignment are required. |
| Daily smoker | Smoking status will be assessed via self-report at screening. Only participants who currently smoke ≥ 10 cigarettes per day can be eligible. |
| Motivated to quit | Reporting motivation to quit smoking (>5 on a 0-10 scale). |
| Exclusion Criteria | |
| Use of other tobacco products | Use of tobacco products, including e-cigarettes, will be assessed during screening. |
| Psychiatric disorders | Currently suicidal or high suicide risk, current or past psychotic disorders of any type, bipolar disorder (I, II, or NOS), schizophrenia or schizoaffective disorder, anorexia, bulimia, alcohol or substance dependence within the last 6 months, patients with comorbid psychiatric conditions that are relative or absolute contraindications to the use of any treatment option in the protocol. These will be assessed by the MINI. |

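### The imbalanced initial avoidance score should enter the target-engagement growth model with a score-by-time term; as C8 reads, the arm-by-time contrast is left unadjusted

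*Combined protocol and SAP*

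**What the plan says.** C8 compares the arms before treatment and states the covariate rule: "variables on which the groups differed were included as covariates in the final analyses if they were significantly related to outcome". It then reports the result: "The only variable that differed between groups was the initial avoidance tendency score ($t(94) = 2.88$, $p = 0.005"), and says of that score, "which was added as a covariate in all analyses". It does not write out the model or say whether the score also interacts with time.

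For target engagement, C8 says "we used intent-to-treat multilevel modeling (MLM) to analyze the growth curve of avoidance tendency scores over the 7 weeks of ABR", with a linear, quadratic or logarithmic time function chosen by AIC and BIC. The initial score appears in one other place: "In exploratory analyses, we examined whether the initial avoidance tendency score moderated the intervention efficacy".

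C2 (Preliminary Studies) describes the smoking pilot. "Participants were 52 smokers who were randomly assigned to four sessions of ABR (experimental) or CTRL training (control"), and it found that "higher levels of approach bias at baseline were associated with greater approach bias reduction over time", at p<.001. No coefficient is given.

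C5c describes a separate baseline AAT and one score at the end of each of the seven training sessions. C8 does not say whether the initial score is the baseline AAT, or whether that score is also a point on the growth curve.

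**The concern.** Target engagement is a question about change: does the avoidance score move differently over the seven weeks in the two arms? In a growth model that is the arm-by-time term. A covariate entered as a main effect shifts each person's whole curve up or down by an amount that depends on the starting score. It does not alter how steeply the curve runs, so any relation between starting score and slope stays in the arm-by-time estimate.

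The imbalanced variable here is the starting level of the very outcome being modelled, and the sponsor's own pilot links starting level to subsequent change. A reader told that the imbalance was controlled would take the engagement result as protected when it may not be. The result could be a false positive, or real engagement could be masked, depending on which arm started higher. Aim 2A, that reduced approach bias mediates the effect on abstinence, leans on it.

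**Working it through.** **Inputs.** t = 2.88 on 94 df, hence 96 people (C8); pilot N = 52 and p<.001 (C2). Assumed: a 48/48 split, two-sided 5% tests, and a range for the correlation ρ between initial score and slope, which the documents do not give.

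**1. The plan's figure.** Two-sided p for t(94) = 2.88 is 0.0049, matching the stated 0.005. The standardised difference is d = 2.88 × √(1/48 + 1/48) = 0.588. A 40/56 split gives 0.596, so the split hardly matters.

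**2. What a main-effect covariate does.** A mixed model with random intercept and slope was fitted to one simulated data set with this imbalance:

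| Model | Arm × time | Arm (level) |
|---|---|---|
| No covariate | −0.0311 (z = −0.632) | 0.297 |
| Score as main effect | −0.0311 (z = −0.632) | −0.026 |
| Score and score × time | +0.0373 (z = 0.826) | −0.054 |

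The main effect moves the level and leaves the slope contrast identical. This is exact for balanced data.

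**3. Size of the bias.** In slope SDs the bias is 0.588 × |ρ|. Its ratio to the standard error, √(2/48) = 0.204, is 2.88 × |ρ|. Given the observed scores, the test statistic is therefore centred at 2.88|ρ| with SD √(1 − ρ²). At 0.44 the centre is 1.27 and the SD 0.898. The chance of passing 1.986 is P(Z > (1.986 − 1.267)/0.898) = P(Z > 0.80), about 21%.

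Simulated false-positive rates with the score as a main effect only:

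| Assumed \|ρ\| | Slope seen through session noise | Correlation applied directly to person slopes |
|---|---|---|
| 0 | – | 5.0% |
| 0.2 | 6–7% | 8.7% |
| 0.3 | 10% | 13.0% |
| 0.44 | 14% | 22.2% |
| 0.6 | 23% | 38.5% |

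With score × time added, the rate is about 4–6% throughout.

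**4. Masking.** Take an assumed true slope effect of 0.6 SD with the imbalance working against it, and the correlation applied directly to person slopes. Power is 65%, 55% and 36% at |ρ| = 0.2, 0.3 and 0.44 with the main effect only, and 81%, 84% and 88% with score × time.

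**5. Does week 0 belong to the curve?** Suppose each person has a stable true score plus independent error, with no treatment effect and linear time.
- Seven session scores only: the error in the week-0 score does not enter the slope. Simulated rates are about 5–6% for reliabilities of 0.3 to 0.8, with no score-by-time term.
- Weeks 0 to 7 as outcomes: the times have mean 3.5 and sum of squares 42, so the slope correlates with the week-0 score at −(3.5/√42) × √(1 − reliability) = −0.54 × √(1 − reliability). At reliability 0.61 that is −0.34, and the rate is about 14%; from reliability 0.8 down to 0.3 it runs from about 9% to 23%.

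**6. What the pilot implies.** If its p<.001 came from a simple correlation with N = 52, then t ≥ 3.496 on 50 df and |r| ≥ 3.496/√(3.496² + 50) = 0.44. But if change was measured from baseline, measurement error alone gives |r| = √((1 − reliability)/2), which is also 0.44 at reliability 0.61.

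**The case against.** The strongest reply is that the premise is read from silence. C8 says covariate, not main effect only, and refers to a published plan not reproduced here. It does not name arm × time as the test either. That stands: the main-effect form is inferred. The inference is reasonable, because C8 calls treatment group a moderator when it means an interaction, and makes the initial score a moderator only in exploratory work. That exploratory analysis may contain score-by-time terms, but it asks whether efficacy varies with the starting score and does not replace the main test.

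Second, a reader might infer that the arm which started further out must show spurious change through regression to the mean. The documents do not support that. If only the seven session scores are outcomes, regression to the mean falls between week 0 and session 1, and the main-effect covariate absorbs it.

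Third, the pilot does not establish a correlation of 0.44 for this trial. Its p may come from a repeated-measures model, and baseline may have been part of the measured change. It makes a link plausible, no more.

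Fourth, the inflation is conditional on the observed imbalance; averaged over randomisations the test keeps its level. That is true, but this imbalance is the one the trial has.

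Last, changing a model after results are known is post hoc. That also stands, and is answered by showing both models and saying why.

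**Conclusion.** The concern holds in conditional form. On the natural reading of C8, the arm-by-time contrast for target engagement is not adjusted for a 0.59 SD imbalance in the starting score. It is then biased if score and slope are related, or if week 0 is an outcome point. The false-positive rate is about 6–9% at a correlation of 0.2, 14–22% at 0.44, and nominal at zero. These percentages are illustrative: they rest on a 48/48 split, two-sided 5% tests, an assumed correlation, and variance settings that the documents do not supply. I also take C8's avoidance score to be C5c's approach bias score with the sign reversed.

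It would go too far to conclude that the slope was certainly unadjusted, that any reported engagement is an artefact, or that the bias favours ABR: C8 gives neither the covariate's form nor the sign of the imbalance. The primary abstinence comparison is outside this argument. This is a worthwhile, cheap improvement to a secondary, mechanistic analysis.

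**What to change.** In C8, state the form in which the initial score enters each model. In the avoidance-score growth model, include initial score × the selected time function and test arm × time there; if week 0 is an outcome point, use a baseline-constrained model instead. Report the main-effect-only model beside it, and say that the change was made after the imbalance was seen. Give the arm means and the direction of the imbalance, and say which measurement is the initial score and whether it lies on the curve.

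The cost is one degree of freedom (two for a quadratic) on data already collected, a few sentences in C8, and a post hoc change that must be disclosed. If the score turns out unrelated to slope, the standard error of the slope contrast grows by a factor of about √(1 + 2.88²/94) = 1.04.

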We have a history of successful recruitment for NIH-funded trials of smoking cessation interventions and will use the approach that has been effective in these studies. Specifically, we will advertise through numerous community organizations that promote quit smoking initiatives and also use social media and Internet outlets to advertise our study. The greater Austin, TX area has a population of 1.9 million. The enrollment period will be 127 weeks (of 156 weeks), allowing sufficient time for start-up activities (12 weeks) and participants to complete the study protocol (17 weeks) and complete data analysis (starting at week 139). Accordingly, we need to enroll 0.8 patients every week or 4 patients every 5 weeks. Currently, we screen, on average, 22.45 individuals weekly (or 112 every five weeks) for ongoing smoking cessation studies. Given the required conversion rate is 4% (4 of 112), we deem this targeted enrollment feasible.

C3c. Screening Procedures

An initial web screen will be performed with all potential participants to determine initial eligibility (e.g., smoking history, motivation to quit). A UT staff member will contact potential participants who appear eligible following screen to provide more details about the study and, if the participant provides informed consent, the staff member will conduct the Mini International Neuropsychiatric Interview (MINI)^{41,42} to assess psychiatric exclusion criteria. Participants who are eligible and remain interested will be enrolled.

C4. Procedures

C4a. Randomization and Baseline Visit

Eligible participants will be randomized to study condition prior to the baseline visit. The project biostatistician, [name], will oversee the randomization. He will use variable-sized permuted block-randomization (block sizes will vary from 4 to 12). Prior to data analyses, [name] will check the balance of randomization and control for any factors that are imbalanced. The baseline visit serves to obtain initial assessments on the outcome and mechanisms variables.

C4b. Interventions

Participants will receive a standard, individual smoking cessation treatment based on the most recent clinical practice guideline from the U.S. Department of Health and Human Services, Treating Tobacco Use and Dependence³. Consistent with the manualized procedures we have employed in past and ongoing NIDA-funded investigations⁴³⁻⁴⁶, the standard intervention (ST) involves a combination of CBT plus NRT.

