As in past an ongoing work⁴³⁻⁴⁶, self-reported smoking status will be assessed during the intervention (weeks 0-7), at posttreatment (week 8), and at 1-month (week 9), 2-month (week 13) and 3-month (week 17) follow-up (i.e., post-quit; see Figure 6). Self-reported abstinence will be verified by expired carbon monoxide (CO). Abstinence at the 2-month (week 13) and 3-month (week 17) follow-up will additionally be verified with saliva cotinine. We will use the timeline follow-back (TLFB) procedure at all assessments to assess cigarette consumption at each day following the previous assessment, which has demonstrated good reliability and validity⁴⁹. Self-reported abstinence will be overridden by a positive carbon monoxide ($\geq 4\text{ppm}$)⁵⁰ or saliva cotinine verification ($>10 \text{ ng/mL}$)⁵¹. If neither CO nor cotinine levels are available to verify abstinence at an assessment, abstinence will be considered missing data⁵². We will employ 7-day point prevalence abstinence (PPA) and prolonged abstinence (PA) as the primary outcomes. PPA will be defined as no smoking, not even a puff, in the 7 days prior to any assessment. Failure to maintain PA at any assessment will be defined by smoking on 7 consecutive days or smoking at least once each week over 2 consecutive weeks⁴⁰.

Figure 6. Assessment Schedule

| | Protocol Weeks | | | | | | |
|--|----------------|----------|----------|-----------|------------------|---------------|-------------------------------|
| | -3,-2,-1 | 0 | 1-4 | 5 | 6 | 8 | 9-17 |
| | End Points | | | | | | |
| | Pre-Screen | Baseline | Pre-Quit | Quit Week | 1-Week Follow-up | Posttreatment | 1-, 2-, and 3-Month Follow-up |
| Screening | | | | | | | |
| Demographics | X | | | | | | |
| Smoking history | X | | | | | | |
| Motivation to quit | X | | | | | | |
| Nicotine dependence (FTND) | X | | | | | | |
| Psychiatric diagnosis and suicide (MINI) | X | | | | | | |
| AIM 1: Efficacy | | | | | | | |
| Self-reported smoking (TLFB) | | X | X | X | X | X | X |
| Carbon monoxide | | X | X | X | X | X | X |
| Saliva cotinine | | | | | | | X ¹ |
| AIM 2: Mechanisms of Action | | | | | | | |
| Craving (QSU-B) | | X | X | X | X | | |
| Approach Bias (AAT; session data) | | X | X | X | | | |

¹ Only assessed at 2- and 3-month follow-up

C5c. Mechanisms of Action

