We will use the same procedures as in ongoing and previous studies^{43–46}. Personnel involved in screening will be certified in diagnostic interviewing. Certification will involve attending a workshop provided by [name] and successful screening of 5 potential participants under supervision of certified personnel.

C6b. Checks of Integrity of Treatment Procedures

Drs. [name] will provide in-person training and supervision to [name], who will deliver the CBT sessions. Adherence scores will be used as part of supervision, which will occur on a monthly basis.

Approach bias retraining latencies will be checked for treatment integrity. Training trials with errors (i.e., participants pushed when they should have pulled and vice versa) and unusual response latencies (i.e., very long (> 2000ms) or very fast (< 200ms) trials) will be dropped. Training integrity for a given session will be considered unacceptable when 20% or more of the trials are dropped. Based on our past experience, we expect high levels of training integrity^{10–12,14}.

C7. Participant Adherence and Incentives for Participation

We will utilize a number of strategies in efforts to promote adherence and retention. Prior to randomization, participants will have completed an extensive screening process. Participants will also be provided a behavioral expectations document informing them of the requirements of their assigned group.

[name], supervised by Drs. [name], will manage retention of the participants. She will be able to meet with participants on 6–7 days of the week for their sessions. If a participant misses a session, she will call to check in, encourage attendance, and help problem solve if a barrier to participation is present. [name] will also monitor adherence to the assessment schedule. She will place reminder calls/emails to participants three days prior to each scheduled follow-up session. Participant self-reported abstinence will be verified for each of these major end point assessments.

Finally, we will provide \$250 per individual (i.e., \$50 for completing each major outcome assessment; weeks 0, 6, 9, 13, and 17) as an incentive for participation in the study. We think this amount is appropriate given the amount of time required for completing the assessments.

C8. Data Analysis

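### Entry as a daily smoker rests on self-report and comes before the first CO reading, so someone not smoking at entry can be counted as a verified quitter after the quit date

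*Combined protocol and SAP*

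**What the plan says.** **Entry.** Figure 7 says "Smoking status will be assessed via self-report at screening" and continues: "Only participants who currently smoke ≥ 10 cigarettes per day can be eligible". Section C3c describes the first step: "An initial web screen will be performed with all potential participants to determine initial eligibility". C5a lists what the online screen collects: demographics, smoking history, the FTND and motivation to quit. Staff contact then adds consent and the MINI for psychiatric exclusions. No CO or cotinine is taken, and no entry threshold for either is set.

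**Order of steps.** Section C4a: "Eligible participants will be randomized to study condition prior to the baseline visit". It gives that visit one purpose: "The baseline visit serves to obtain initial assessments on the outcome and mechanisms variables". Figure 6 starts both CO and TLFB at week 0, with neither at pre-screen. Nothing says what happens if baseline CO is low.

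**Outcome.** Section C5b: "Self-reported abstinence will be overridden by a positive carbon monoxide" (4 ppm or more) or, at weeks 13 and 17, by saliva cotinine above 10 ng/mL. PPA requires seven days without any smoking.

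**Incentive and recruitment.** C7 pays $250, as $50 at each of five assessments through week 17, "as an incentive for participation in the study". C3b recruits partly through social media and the internet.

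**The concern.** The plan does not accept self-report as sufficient at the outcome end but does at the entry end. The biochemical check is built to catch a smoker who claims to have quit. It cannot catch a non-smoker who claimed to smoke, because that person's low CO agrees with the later report of abstinence.

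Such an entrant reports smoking before the quit week and abstinence after it. On the outcome data this looks like a successful quit at exactly the point where C8 places the discontinuity in abstinence and lets treatment group act on it. Training had nothing to change in that person, so the entrant adds an apparent success unrelated to treatment.

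C2 makes efficacy estimation the primary aim, and the Abstract and Specific Aims say the effect sizes will inform a larger trial. Inflated absolute rates and a diluted contrast would carry into that trial's planning.

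**Working it through.** **Inputs.** From C8: 42% abstinence in ST+ABR, effect size w = .238, N = 100, power stated as above 0.80. The control rate is not given there. Assumed here: 50 per arm, two-sided alpha 0.05, a share f of entrants in each arm not smoking at entry, and all of them scored abstinent after the quit date. The documents give no value for f, so a range is shown.

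**Reproducing the plan's figures.** With w = (p1 − p2) / (2√(p̄(1 − p̄))), p1 = 0.42 and p2 = 0.20: p̄ = 0.31 and w = 0.22 / (2√(0.31 × 0.69)) = 0.2378. The stated .238 therefore implies a 20% control rate, inside the 15-35% cited for standard care. Power for a comparison at one time point is Φ(√100 × 0.2378 − 1.96) = Φ(0.418) = 0.66, so the stated 0.80 is not reproduced that way. A repeated-measures analysis could reach it, but the needed correlation is not in the documents. The point made here does not depend on that figure.

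**Dilution.** Observed rate p′ = (1 − f)p + f.

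| f | ST+ABR | ST+CTRL | Difference (points) | Odds ratio | Power, one time point |
|---|---|---|---|---|---|
| 0 | 42.0% | 20.0% | 22.0 | 2.90 | 0.66 |
| 3% | 43.7% | 22.4% | 21.3 | 2.69 | 0.62 |
| 5% | 44.9% | 24.0% | 20.9 | 2.58 | 0.59 |
| 10% | 47.8% | 28.0% | 19.8 | 2.35 | 0.53 |

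For f = 5%: 0.95 × 0.42 + 0.05 = 0.449 and 0.95 × 0.20 + 0.05 = 0.240. The difference shrinks by the factor (1 − f): 0.95 × 22.0 = 20.9.

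**Chance imbalance.** Suppose five such entrants among 100 are randomised 50:50. The chance of a 4-1 or 5-0 split, in either direction, is 2 × [C(50,5) + C(50,4) × 50] / C(100,5) = 27,267,520 / 75,287,520 = 0.362.

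One entrant adds at most 1/50 = 2 points to an arm. The net expected addition is smaller, because the place would have been abstinent with probability p anyway: (1 − 0.42)/50 = 1.16 points in ST+ABR and (1 − 0.20)/50 = 1.60 in ST+CTRL.

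- 4-1 split: 22.0 + 4(1.16) − 1.60 = 25.0, or 22.0 + 1.16 − 4(1.60) = 16.8.
- 5-0 split: 22.0 + 5(1.16) = 27.8, or 22.0 − 5(1.60) = 14.0.

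**Scale.** The standard error of the difference at 42% v 20% is √(0.42 × 0.58/50 + 0.20 × 0.80/50) = 0.090, about 9 points.

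**Cotinine timing.** C4b gives 6 + 1 + 1 = 8 weeks of patch from week 5, so use runs up to about week 13. The week-17 test falls after the planned course.

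**The case against.** The strongest reply is that the problem is hypothetical, small and equal in both arms. No document shows that any non-smoker entered. The screen asks for rate, brand, nicotine content, past quit attempts and age of onset, plus the FTND, which is harder to fake than one web item. Recruitment also runs through community quit-smoking organisations and physician referral, and payment is spread over five assessments. At 5% the expected loss is 1.1 points against a standard error of 9. Uneven splits are ordinary sampling variation. The table compares proportions at one time point, whereas C8 models a jump and a post-quit slope. C8 is also written in the past tense and reports a baseline test, so a new entry rule may come too late for this trial.

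Most of this stands as a limit on size. It does not remove the gap, since every screening item listed is still self-report. Nor does the model avoid it: an entrant who reports smoking and then abstinence contributes to the jump.

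A reader might infer more than the documents support:

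- **That such a person is scored abstinent at every visit.** Abstinence must first be self-reported, and someone posing as a smoker would report smoking before the quit week. After it, patch nicotine may push week-13 cotinine over the cut-off (an assumption about the assay).
- **That anyone who overstates consumption becomes a false quitter.** Someone who keeps smoking fails the PPA definition and can be caught by CO or cotinine. Someone who smoked less than claimed and then stops is a real quitter.
- **That one arm is favoured.** The gap is the same in both arms; imbalance is by chance.
- **That an imbalance of three entrants shifts the result by 6 points.** That counts a gross 2 points each. The net result of a 4-1 split is 25.0 or 16.8, about 4.1 points either side of the expected 20.9.

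**Conclusion.** The concern holds as a limited design weakness. Smoking status at entry is unverified, randomisation comes before the first CO reading, and the later check cannot detect an entrant who was not smoking. Such a person can count as a verified quitter at post-quit visits where abstinence is reported, with week-13 cotinine uncertain because of the patch.

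The size is unknown. Under the stated assumptions the difference falls from 22.0 points to 21.3, 20.9 or 19.8 at 3%, 5% or 10%, while the control rate rises from 20% to 22.4%, 24.0% or 28.0%. In points, the effect on absolute control rates is larger than the effect on the contrast, which matters for planning the follow-up trial. The calculation takes all such entrants as always scored abstinent, a worst case for each f, and rests on an implied 20% control rate. It does not show that the trial's result is biased towards either arm.

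**What to change.** 1. **Entry rule (Figure 7, C3 and C4a).** State that current smoking is confirmed at the baseline visit by TLFB and expired CO of at least 4 ppm, the cut-off the plan already uses, with one repeat allowed, and that randomisation follows this check. State also that CO confirms recent smoking only; the level of 10 cigarettes per day still rests on self-report. If enrolment is complete, this serves mainly the follow-up trial.

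2. **Participants already enrolled (C8).** List those with baseline CO below 4 ppm by arm and repeat the abstinence analysis without them. Label it a sensitivity analysis: under the current order this CO was taken after randomisation, although before training began, so the subset is not defined by a pre-randomisation measurement.

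**Cost.** No new procedure, since CO and TLFB are already scheduled at week 0. An occasional genuine smoker with a low reading needs a repeat breath test, and randomisation moves to the end of the baseline visit. The second item needs only data already scheduled for collection.
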